3.4 Research Evaluation Plan

3.4.1 Baseline evaluation

3.4.2 Pre medication evaluation of treatment plan (starting from d1, once every 6 weeks, completed each time before administration)

Inspection items	Inspection time and related instructions
Physical examination, medical history	
Medical history collection
 
Physical examination items must include: heart rate, blood pressure, respiratory rate, body temperature, height, weight, and neurological examination
 
Emphasis should be placed on inquiring about possible adverse reactions of Sintilimab

Peripheral blood routine	
The blood routine test must include: red blood cell count (RBC), hemoglobin (Hb), white blood cell count (WBC), and white blood cell classification count (absolute neutrophil and lymphocyte counts are required), hematocrit (HCT), and platelet count (PLT).

Blood biochemical examination	
The blood biochemistry items must include: blood electrolytes (K Na Ca Mg Cl HCO3- is necessary), ALT, AST, γ - GT, total bilirubin, direct bilirubin, amylase, lipase, creatinine, urea T nitrogen, serum albumin, blood glucose

thyroid function	
Thyroid function items must include: T3, T4,

	fT3, fT3, TSH
urinalysis	Urine routine items must include: urine specific gravity (SG), urobilinogen (URO), occult blood (BLD), white blood cells (WBC), urine protein (PRO), urine glucose (GLU), bilirubin (BIL), ketone bodies (KET), urine red blood cells (RBC), and urine color (COL).
Electrocardiogram examination	Twelve lead electrocardiogram
Blood and tissue specimens for biomarker research	Before treatment and before each efficacy evaluation (blood samples)

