This study is a prospective single blind randomized controlled clinical trial of maintenance therapy with Xindilimab based on peripheral CD8TEX screening after standard radiotherapy and chemotherapy for locally advanced head and neck tumors. Synchronous radiotherapy and chemotherapy are routine standard treatments and do not require the use of immunotherapy drugs in this study. Blood samples were collected before and after radiotherapy, and participants were screened and evaluated according to the inclusion and exclusion criteria of the protocol within 28 days before randomization. Patients who

agree to participate in this study will sign an informed consent form (ICF) prior to the screening process. After completing all screening activities, eligible participants can start receiving study treatment. According to the estimated sample size, a total of 104 patients are planned to be enrolled and randomly assigned equally to the experimental group and control group. The treatment cycle for the study is 21 days. The experimental group starts treatment within one month after the end of radiotherapy and chemotherapy. On the first day of each cycle, intravenous treatment with Sintilimab is given, with a cycle of 21 days. It is expected to be administered for a total of 18 cycles, or until the disease progresses; The control group received placebo treatment. The experimental group underwent routine blood tests, liver and kidney function, myocardial enzyme spectrum, thyroid function, electrocardiogram every 2 cycles, and CT scans every 4 cycles to evaluate toxic side effects; The control group underwent the same frequency of follow-up and observation. The study started on January 1, 2024 and ended on January 1, 2027, to explore the efficacy of maintenance therapy with Xindilimab after radiotherapy and chemotherapy for locally advanced head and neck tumors.

Research plan:

Intravenous infusion of Sintilimab, D1, once every 3 weeks

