3.4.3 Efficacy evaluation

Inspection items	Inspection time and related instructions
Imaging examination	Complete baseline assessment within 1 month before treatment, and treat every 3 months Chest and abdominal CT examination evaluation

3.4.4 Testing items and time after discontinuation/withdrawal from the study (once every 9 weeks since the last medication use)

Inspection items	Inspection time and related instructions
Telephone follow-up	Telephone follow-up every two months

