- Before administration, the injection medication should be visually inspected for the presence of suspended particles and discoloration. This product is a clear to slightly milky, colorless to light yellow liquid with no foreign objects. If visible particles are observed, the medicine bottle should be discarded.
- Extract 2 bottles of this product injection (200mg) and transfer them to an intravenous infusion bag containing 9mg/ml (0.9%) sodium chloride solution. Prepare a final concentration range of 1.5-5.0mg/ml. Gently flip the diluent and mix well.
- From a microbiological perspective, this product must be used immediately upon dilution and should not be frozen. The stability study of this product shows that it can be stored in dark at 2-8 ° C for 24 hours, including a maximum of 6 hours under indoor light at 20-25 ° C (6 hours including administration time). After refrigeration, the medication bottle and/or intravenous infusion bag must be restored to room temperature before use. The infusion tube used during infusion must be equipped with a sterile, heat free, low protein binding infusion tube filter (pore size 0.2) μ m). The infusion time is within 30-60 minutes.
- Do not use the same infusion tube to administer medication simultaneously with other medications.
- This product is for one-time use only. Any unused medication remaining in the medication bottle must be discarded.

Medication adjustment of Sintilimab

Throughout the entire research process, it is not allowed to adjust the dosage of Xindilimab. The principles of suspending and permanently stopping Xindilimab administration are shown in the table below.

3.5.2 信迪利单抗暂停给药和永久停药原则

Adverse events with Sintilimab	Severity	Dose adjustment
pneumonia	Grade 2	Suspend administration ^a
	Grade 3 or 4 or recurrent level 2	Permanent discontinuation of medication
Diarrhea/Colitis	Grade 2 or 3	Suspend
	Grade 4	Permanent
hepatitis	For subjects with normal baseline ALT, AST, or TBIL, level 2 AST, ALT (3-5 times ULN), or TBIL (1.5-3 times ULN) were elevated; For subjects with baseline AST, ALT, or TBIL>ULN, an increase of $\geq 50\%$ in AST, ALT, or TBIL (meeting level 2 requirements) and a duration of <7 days is required	Suspend administration ^a

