	For subjects with normal baseline ALT, AST, or TBIL, grade 3 or 4 AST, ALT (>5x ULN), or TBIL elevation (>3x ULN); For subjects with baseline AST, ALT, or TBIL>ULN, AST, ALT, or TBIL increase $\geq 50\%$ (meeting level 3 or 4 requirements) and duration ≥ 7 days	Permanent discontinuation of medication
nephritis	Grade 2 or Grade 3 elevated blood creatinine	Suspend administration ^a
	Grade 4 elevated blood creatinine	Permanent discontinuation
Endocrine disorders	Symptomatic grade 2 or 3 hypothyroidism	Suspend administration ^a
	Grade 2 or 3 hyperthyroidism	
	Grade 2 or 3 pituitary inflammation	
	Grade 2 adrenal insufficiency	
	Grade 3 hyperglycemia or type 1 diabetes	Permanent discontinuation of medication
	Grade 4 hypothyroidism	
	Grade 4 hyperthyroidism	
	Grade 4 pituitary inflammation	
	3rd or 4th grade adrenal insufficiency	
Skin adverse reactions	Grade 4 hyperglycemia or type 1 diabetes	
	Grade 3	Suspend administration ^a
thrombocytopenia	Level 4, Stevens Johnson syndrome (SJS) or toxic epidermal necrolysis (TEN)	Permanent discontinuation
	Grade 3	Suspend
	Grade 4	Permanent

Other immune related adverse reactions	Level 3 or 4 elevated blood amylase or lipase	Suspend administration ^a
	Grade 2 or 3 pancreatitis	
	Grade 2 myocarditis c	Permanent discontinuation of medication
	Other immune related adverse reactions that occur for the first time at level 2 or 3	
	Grade 4 pancreatitis or any level of recurrent pancreatitis	
	Grade 3 or 4 myocarditis	
Recurrent or persistent adverse reactions	Grade 3 or 4 encephalitis	Permanent discontinuation of medication
	Other immune related adverse reactions that first occurred at level 4	
	Recurrent grade 3 or 4 (excluding endocrine disorders)	
	Grade 2 or 3 adverse reactions within 12 weeks after the last administration	
	Not improved to level 0-1 (excluding endocrine diseases)	Permanent discontinuation of medication
	Failure of corticosteroids to decrease to $\leq 10\text{mg/day}$ prednisone equivalent dose within 12 weeks after the last administration	

Table: Suspension and permanent discontinuation of Sintilimab regimen

a: Resumption of medication after symptom improvement to level 0-1 or baseline level.

b: Pituititis, adrenocortical insufficiency, thyroid insufficiency/hypothyroidism and type 1 diabetes can be reused when they are fully controlled and only need physiological hormone replacement treatment.

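### Scheduled safety laboratory tests and adverse-reaction inquiry come every 42 days for a drug infused every 21 days, so 9 of 18 planned doses have no scheduled pre-dose result

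*Protocol*

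**What the plan says.** Dosing is fixed in protocol section 3.3: "Intravenous infusion of Sintilimab, D1, once every 3 weeks", in 21-day cycles. On duration it says "It is expected to be administered for a total of 18 cycles", with earlier stopping at progression. The control arm receives placebo and is followed at the same frequency.

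Monitoring appears in two places:

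- Section 3.3 requires "routine blood tests, liver and kidney function, myocardial enzyme spectrum, thyroid function, electrocardiogram every 2 cycles".
- The heading of section 3.4.2 sets the pre-medication evaluation as "starting from d1, once every 6 weeks, completed each time before administration". Its table covers history and physical examination, blood count, biochemistry (including transaminases, bilirubin, creatinine, glucose, amylase and lipase), thyroid function, urinalysis and ECG. The adverse-reaction inquiry is in the same table: "Emphasis should be placed on inquiring about possible adverse reactions of Sintilimab".

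Section 3.5.2 then lists when sintilimab is suspended or stopped for good. Several rows are defined by laboratory values. One suspension criterion for hepatitis, in subjects with normal baseline values, is "level 2 AST, ALT (3-5 times ULN), or TBIL (1.5-3 times ULN) were elevated". The nephritis row suspends at "Grade 2 or Grade 3 elevated blood creatinine". Other rows act on graded hyperglycaemia, thrombocytopenia, and raised amylase or lipase.

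**The concern.** The rules in 3.5.2 can work only if the investigator knows the laboratory grade when deciding whether to infuse. Raised transaminases, creatinine, glucose or lipase and a falling platelet count may all be silent. If the plan schedules no test before every second infusion, a patient who already meets a suspension or discontinuation criterion can receive one more dose while the site follows the protocol exactly.

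The hepatitis row shows the mismatch most clearly. For subjects whose baseline values exceed the upper limit of normal, the split between suspension and permanent discontinuation depends partly on whether the rise has lasted less than 7 days or at least 7 days. Tests 42 days apart cannot supply that duration.

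What is at stake is patient safety during treatment.

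**Working it through.** **Inputs.** Cycle length 21 days, dosing on day 1 of each cycle, and 18 expected cycles (all 3.3). Safety tests every 2 cycles (3.3). Pre-medication evaluation every 6 weeks from day 1 (3.4.2). Planned enrolment 104 (3.3).

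**Do the two monitoring statements agree?** 2 cycles × 21 days = 42 days, and 6 weeks × 7 days = 42 days. They agree.

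**Dose days.** Dose k falls on day 21(k − 1) + 1, for k = 1, ..., 18: days 1, 22, 43, ..., 358.

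**Evaluation days.** Evaluation j falls on day 42j + 1, for j = 0, ..., 8: days 1, 43, 85, 127, 169, 211, 253, 295 and 337. These nine evaluations coincide with doses 1, 3, 5, ..., 17.

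**Doses without a scheduled evaluation.** Doses 2, 4, 6, ..., 18, on days 22, 64, 106, 148, 190, 232, 274, 316 and 358. That is 18 − 9 = 9 of 18, or 50%. At each one the latest scheduled result is 21 days old (for example, 22 − 1 = 21).

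**Shorter treatment.** With n uninterrupted cycles the count is floor(n/2): 2 of 4, 4 of 8, 6 of 12.

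**Could the heading of 3.4.2 mean every dose?** Its closing words, on completion before administration, might suggest so. That reading would conflict with the 6-week interval in the same heading and with the 2-cycle interval in 3.3. The sensible reading is that each 6-weekly evaluation must be finished before that day's infusion.

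**Is anything else scheduled at the even doses?** The adverse-reaction inquiry is in the 6-weekly table. Section 3.6 requires a medication review and a question about new medicines at each visit, which does not reveal a silent laboratory change. Section 7.3 requires timely handling of adverse events, but an event must first be noticed.

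**With an evaluation every 21 days.** 18 of 18 doses are covered instead of 9 of 18.

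**The case against.** The strongest reply is that no stated requirement is breached. Section 3.5.2 says what to do once a grade is reached, not how often to look, and nothing in the protocol demands a result before each dose. The figure 9 of 18 restates the interval and does not measure risk. The count also assumes no interruption: after a suspension, the resumption rule requires the event to return to grade 0–1 or baseline, which for a laboratory event implies repeat testing off the 42-day grid. Unscheduled tests are not restricted, a physician must be available during infusions, and changes in CTCAE grade must be recorded.

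Most of this stands, and it limits the claim. But the resumption rule helps only after an abnormality has been found, and none of the other safeguards would reveal a silent one before an even-numbered dose.

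A reader might also infer three stronger points that the protocol does not support:

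- **That 3.3 and 3.4.2 conflict over myocardial enzymes.** Section 3.3 requires them and the 3.4.2 table does not list them, but the biochemistry list there is worded as a minimum. The enzymes are missing from the table, not from the protocol.
- **That no laboratory test follows the last dose.** On the 3.4.2 grid the last evaluation (day 337) precedes the last dose (day 358) by 21 days, and the only row shown in 3.4.4 is "Telephone follow-up every two months". However, the heading of 3.4.4 speaks of testing items every 9 weeks after the last medication, and the 2-cycle rule in 3.3 could be read as placing a test after cycle 18, on day 21 × 18 + 1 = 379. The text is unclear, so a gap is not established.
- **That doses will in fact be given against the rules.** The protocol gives no rate of laboratory abnormalities, so that number cannot be calculated.

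**Conclusion.** The point holds as a weakness in safety design. Sections 3.3 and 3.4.2 consistently fix a 42-day grid against 21-day dosing, so half of the planned infusions (9 of 18) have no scheduled pre-dose laboratory result or adverse-reaction inquiry, while 3.5.2 makes dosing depend on grades that can change silently. Following the plan as written can lead to an infusion that its own rules would withhold.

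The count is exact for a patient who completes 18 cycles without delay and is floor(n/2) for n uninterrupted cycles. It describes scheduled coverage, not harm. It is not an internal contradiction, and the PFS comparison is unaffected. The change is worth making because it is cheap and the safety gain is specific.

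**What to change.** In 3.3 and 3.4.2, require the following before every 3-weekly infusion, in both arms:

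- results for blood count, ALT, AST, bilirubin, creatinine, glucose, and amylase and lipase;
- a brief adverse-reaction inquiry.

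Thyroid function and ECG can stay at 6-weekly intervals.

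The cost is protocol wording plus up to nine extra routine draws per patient, at most 104 × 9 = 936 in the trial and fewer where treatment stops early. The draws fall at infusion visits that already take place, and with equal allocation up to half of them are in placebo patients.

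As an editorial alignment only, add the myocardial enzymes already required by 3.3 to the 3.4.2 table. The sponsor could also clarify in 3.4.4 which tests, if any, follow the last dose.

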3.4.3 Efficacy evaluation

Inspection items	Inspection time and related instructions
Imaging examination	Complete baseline assessment within 1 month before treatment, and treat every 3 months Chest and abdominal CT examination evaluation

3.4.4 Testing items and time after discontinuation/withdrawal from the study (once every 9 weeks since the last medication use)

Inspection items	Inspection time and related instructions
Telephone follow-up	Telephone follow-up every two months

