A prospective randomized single blind controlled study on maintenance therapy with Sintilimab after radiotherapy and chemotherapy for locally advanced head and neck tumors based on peripheral blood CD8TEX detection

Main researcher: [name]

Plan version number: 1.0 version

Date of formulation: January 25, 2024

Main research unit: Second Affiliated Hospital of Zhejiang University

1. Introduction to research background:

Head and neck squamous cell carcinoma (HNSCC) includes cancers of the mouth, oropharynx, larynx and hypopharynx. The incidence rate ranks the sixth with a mortality rate of 40-50%. It is a serious disability and life-threatening disease. Due to the unique anatomical location, the surgical disability rate of HNSCC is high, which seriously affects the quality of life of patients. Radiation therapy is a very important local treatment for malignant tumors. Radiation therapy not only protects organ function and has cosmetic effects, but also has a long-term survival comparable to surgical treatment for early HNSCC patients receiving radiation therapy. However, over 60% of HNSCC patients are initially diagnosed as locally advanced. For patients with locally advanced stage who cannot undergo surgery, the current standard treatment regimen is synchronous radiotherapy and chemotherapy (CRT) or synchronous targeted treatment with cetuximab, followed by clinical follow-up. However, there are still relatively high rates of local recurrence or distant metastasis in patients with locally advanced head and neck tumors after radiotherapy and chemotherapy. The 3-year PFS rate is about 60%, 50% of relapses occur within 2 years after radiotherapy and chemotherapy, 20% to 30% of patients experience distant metastasis, and the overall 5-year survival rate is less than 50%. Therefore, it is necessary to further optimize the maintenance treatment plan after radiotherapy and chemotherapy, in order to improve the clinical cure rate of patients with locally advanced head and neck tumors.

Immunotherapy has achieved significant breakthroughs in recurrent and metastatic head and neck tumors. Studies on various tumor models have shown that tumor infiltration of PD-1+CD8+depleted T cells (CD8+TEX) is an important mechanism for the reduction of anti-tumor function and tumor progression in the body. Immunotherapy can reactivate T cell responses by blocking the PD-1 pathway. A

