At present, there are no research reports on the changes of CD8+TEX cells in the tumor immune microenvironment after radiotherapy. In our preliminary research, we found in the HNSCC mouse tumor model that the proportion and quantity of PD-1+CD8+TEX cells in the tumor and peripheral blood significantly increased with the prolongation of time after radiotherapy, and the combination of immunotherapy at the end of radiotherapy or 7 days after radiotherapy had the best therapeutic effect. We further tested the proportion of TEX in human peripheral blood and the expression level of PD1 during and after synchronous radiotherapy and chemotherapy, and found a similar trend as in the mouse model. So we speculate whether the proportion of peripheral blood CD8+TEX cells and the expression level of PD1 can be used as a suitable screening for immunotherapy. In the early stage, we retrospectively analyzed three patients who underwent immune maintenance therapy after synchronous radiotherapy and chemotherapy, and found that they have been followed up for three years, and no PFS time has been obtained. This study aims to ensure that patients receive standard treatment. By screening the proportion of CD8+TEX cells in peripheral blood and the expression level of PD1, patients with upregulation of CD8TEX in peripheral blood after radiotherapy or patients with PD1 expression levels higher than normal were randomly divided into two groups: one group received maintenance therapy for immunity, and the other group received placebo comparison to evaluate PFS time.

2. Research Purpose

2.1 Research Purpose:

A prospective randomized single blind controlled study on maintenance therapy with Sintilimab after radiotherapy and chemotherapy for locally advanced head and neck tumors

2.2 Main study endpoints:

Evaluation of progression free survival (PFS) and 1-year progression free survival (PFS) in two groups of patients with locally advanced head and neck tumors after radiotherapy and chemotherapy (using RECIST 1.1 criteria)

2.3 Secondary study endpoints:

Evaluation of overall survival (OS), safety and tolerability, changes in quality of life relative to baseline, and time to deterioration in maintenance therapy with Xindilimab in patients with locally advanced head and neck tumors after radiotherapy and chemotherapy (EORTC QLQ-C30 and H&N-35)

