The primary safety analysis will be conducted based on subjects who experience toxicity (as defined by CTCAE standards). CTCAE version 5.0 will be used to evaluate safety through reported adverse events. The relationship between adverse events and drugs, onset time, duration of events, their resolution, and any concomitant medication will be recorded. Adverse events (AEs) will be analyzed, including but not limited to all AEs, SAEs, lethal AEs, and laboratory changes.

2.4 Exploratory study endpoint:

Explore biomarkers for predicting efficacy and adverse reactions, and obtain better guidance on the combination therapy and safety of immunotumor drugs. In order to identify novel biomarkers, we collected biological samples: 10-20ml of blood (before treatment and during efficacy evaluation) to support the analysis of cellular components (such as DNA, proteins, etc.), such as whole exome gene testing, TMB, PD-L1, MRD, etc.

3. Research design and methods:

3.1 Inclusion criteria:

- (1) Male or female, age ≥ 18 years old, ≤ 75 years old.
- (2) Localized advanced head and neck tumors with T3 or N+ or above that have been histologically confirmed as inoperable.
- (3) Patients undergoing synchronous radiotherapy and chemotherapy
- (4) ECOG physical fitness status ranges from 0 to 1 point.
- (5) The expected lifespan is at least 12 weeks.
- (6) At least one measurable lesion
- (7) Hematology examination absolute neutrophil count (ANC) $>1.5 \times 10^9/L$, hemoglobin $>8g/dL$ and platelets $>100 \times 10^9/L$ (based on the normal value of the clinical trial center).
- (8) Prothrombin time (PT) <1.5 times the upper limit of normal value and normal thromboplastin time (APTT) <1.5 times the upper limit of normal value.
- (9) Laboratory tests show that serum creatinine is less than or equal to 1.5 times the upper limit of the normal reference range (if serum creatinine increases, 24-hour urine must be collected, except for those with a 24-hour creatinine clearance rate $>50ml/min$).

- (10) When there is no liver metastasis, ALT or AST is less than or equal to 2.5 times the upper limit of the normal reference range, and serum total bilirubin is less than or equal to 1.5 times the upper limit of the normal reference range; For patients with liver metastasis, ALT or AST is less than or equal to 5 times the upper limit of the normal reference range, and serum total bilirubin is less than or equal to 3 times the upper limit of the normal reference range.

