c: For abnormal results in Level 4 laboratory tests, the decision to terminate medication should be based on accompanying clinical symptoms/signs and the researcher's clinical judgment.

The maximum interval allowed for drug suspension is 12 weeks. If the subject cannot recover to a state where they can reuse Sintilimab within 12 weeks, they will permanently discontinue Sintilimab and enter the follow-up phase. Excluding the following two situations:

1) Due to the use of glucocorticoids in the treatment of irAE, the process of reducing glucocorticoids resulted in the suspension of Sintilimab for more than 12 weeks. In this case, it is

necessary to discuss with the medical manager of the sponsor to decide whether to continue treatment with Sintilimab. The imaging examination for evaluating the therapeutic effect is carried out according to the plan and is not affected by the suspension of medication.

2) Due to the treatment of AE unrelated to Xindilimab, Xindilimab was temporarily suspended for more than 12 weeks. In this case, it is necessary to discuss with the sponsor to decide whether to continue treatment with Sintilimab. The imaging examination for evaluating the therapeutic effect is carried out according to the plan and is not affected by the suspension of medication.

The principle of restoring Sintilimab

When resuming the use of Sintilimab, relevant AEs need to be restored to level 0-1 or baseline, with an ECOG PS score of 0-1.

Management of infusion reactions related to Sintilimab

Xindilizumab may cause severe or life-threatening infusion reactions, including severe hypersensitivity or allergic reactions. Signs and symptoms usually appear during or shortly after drug infusion, and can usually be completely resolved within 24 hours of completion of infusion.

The management guidelines for infusion reactions associated with Sintilimab are shown in Table 2.

NCI CTCAE classification	Treatment	Perform pre-treatment medication during subsequent administration
Grade 1 Mild reactions; No need to interrupt infusion; No intervention required	According to the patient's medical indications, strengthen monitoring of their vital signs until the researchers believe that the subject's condition is stable.	None

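### The scheduled efficacy scan names only chest and abdomen, although the primary endpoint is RECIST 1.1 PFS in head and neck tumours

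*Protocol*

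**What the plan says.** Protocol section 2.2 makes PFS and 1-year PFS the primary endpoints, "in two groups of patients with locally advanced head and neck tumors after radiotherapy and chemotherapy (using RECIST 1.1 criteria"). Section 3.1 admits inoperable locally advanced head and neck tumours and requires, in criterion (6), "At least one measurable lesion".

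Imaging appears in three places:

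- Section 3.4.3, the efficacy evaluation table, asks for a baseline assessment within one month before treatment and then: "treat every 3 months Chest and abdominal CT examination evaluation".
- Section 3.3 asks for "CT scans every 4 cycles to evaluate toxic side effects", with the same frequency of follow-up in the control group. No body region is given.
- The text on suspended dosing, after the table in section 3.5.2, says: "The imaging examination for evaluating the therapeutic effect is carried out according to the plan". Again no region is given.

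On treatment duration, section 3.3 says: "It is expected to be administered for a total of 18 cycles", with 21-day cycles, or until progression.

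**The concern.** In this population the measurable lesions are expected to be the primary tumour and the neck nodes. RECIST 1.1 progression is judged by re-measuring such lesions over time. The efficacy schedule names two body regions and leaves out the one where the disease lies.

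The omission touches a main component of the endpoint. The introduction to the protocol says that after radiotherapy and chemotherapy "there are still relatively high rates of local recurrence or distant metastasis in patients with locally advanced head and neck tumors". If the scheduled scan does not cover the site of local recurrence, those events are either missed or dated by whatever unscheduled finding brings them to light. Recorded PFS and 1-year PFS would then be too high, and fewer events would be available for the comparison between arms. Scans that were never taken cannot be recovered at analysis, so a statistical analysis plan cannot repair this.

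**Working it through.** **Does any other section supply head and neck imaging?**

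| Protocol section | What it provides | Head and neck named? |
|---|---|---|
| 3.3 | CT every 4 cycles; stated purpose is toxicity | No region given |
| 3.4.1 | Heading only in the readable text | Cannot be judged |
| 3.4.2 | "Physical examination items must include: heart rate, blood pressure, respiratory rate, body temperature, height, weight, and neurological examination" | Not listed, not excluded |
| 3.4.3 | CT every 3 months for efficacy | No: chest and abdomen only |
| 3.4.4 | Telephone follow-up after discontinuation | No imaging listed |
| After the 3.5.2 table | Efficacy imaging as planned | No region; the efficacy schedule is 3.4.3 |

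No readable section specifies CT, MRI, PET or endoscopy of the head and neck.

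**How many scans are affected?** Treatment lasts 18 × 21 = 378 days.

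- Every 4 cycles is 4 × 21 = 84 days: scans at days 84, 168, 252 and 336, which is 4 scans. The next would fall on day 420, after treatment.
- Every 3 months is about days 91, 183, 274 and 365, also 4 scans.

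The two statements may describe the same scan, but the protocol does not say so. On either schedule, none of the four names the head and neck.

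**What share of events is at risk?** The protocol does not allow this to be derived. One might subtract its 20% to 30% distant metastasis from the 40% of patients with an event by 3 years. However, the metastasis figure has no time frame, and the remaining events include deaths.

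**Illustration.** Inputs from the protocol: 3-year PFS of about 60% (section 1) and 104 patients (section 3.3). Assumptions: constant hazard, the same PFS in both arms and all patients followed for one year.

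- Hazard = −ln(0.60)/3 = 0.1703 per year.
- True 1-year PFS = exp(−0.1703) = 0.8434.
- 1-year event risk = 1 − 0.8434 = 0.1566.
- Expected events = 104 × 0.1566 = 16.3.

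Let q be the assumed share of those events that are locoregional and still unrecorded at one year. Recorded 1-year PFS = 1 − 0.1566 × (1 − q), and events lost = 16.3 × q.

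| q (assumed) | Recorded 1-year PFS | Events lost |
|---|---|---|
| 0 | 84.3% | 0 |
| 12.5% | 86.3% | 2.0 |
| 25% | 88.3% | 4.1 |
| 50% | 92.2% | 8.1 |

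**The case against.** The strongest reply is that the text is damaged and the omission may be apparent only. The cell in section 3.4.3 is a compressed translation, section 3.4.1 is a bare heading, and a lost baseline table could have named the disease site. That limit stands for baseline imaging, and no claim is made about it here. It does not reach the on-treatment row, which is readable and names its regions.

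A second reply is that specifying RECIST 1.1 already obliges sites to follow the measurable lesions wherever they lie, so the CT row only names the systemic scan. Many sites may well read it so. But then sections 2.2 and 3.4.3 pull in different directions, and a site that follows 3.4.3 to the letter complies with the protocol without imaging the tumour.

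Third, silence is not exclusion. The CT in section 3.3 might cover the neck, the physical examination list is a minimum, and clinical follow-up would detect some recurrences. This is fair, and it is why q is below 100% and cannot be fixed from the document. Detection by those routes would still be unscheduled, or not required by the protocol.

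Fourth, the event-loss figures rest on an assumed q and on a background PFS that is not specific to this biomarker-selected cohort. They show scale only, and the conclusion does not depend on them.

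Finally, the same frequency applies to both arms, so no bias between arms is demonstrated. That also stands: what follows directly is inflated PFS and lost events in both arms.

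**Conclusion.** The concern holds. As written, the efficacy schedule does not provide for serial assessment of the anatomical site that carries the disease under study, which contradicts a RECIST 1.1 primary endpoint requiring measurable lesions. This is more than missing detail, because the regions are stated and the relevant one is not among them. It should be corrected as a priority, since the loss is irreversible for each patient scanned under the present wording.

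How much PFS would be overstated is not known. Under the stated assumptions, 1-year PFS would be raised by about 2 to 8 percentage points and about 2 to 8 of some 16 first-year events would be lost. The conclusion rests on the readable text. It would fall only if a section that cannot be read specifies head and neck imaging at the efficacy evaluations during treatment.

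**What to change.** In section 3.4.3, extend the scheduled CT to cover the head and neck as well as the chest and abdomen, at baseline and at every efficacy evaluation. State that each patient is followed with the same modality throughout and that the schedule is identical in both arms. The essential element is naming the region. If another modality is preferred for the head and neck, the same consistency rule should apply.

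Reconcile section 3.3 with section 3.4.3: say whether the CT every 4 cycles and the 3-monthly CT are the same scan, name the region, and state that it serves efficacy as well as toxicity.

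The cost is protocol wording and a longer scan range at CT visits that already exist. No extra visits, staff or patients are needed. The downside is some added contrast and radiation at those visits.
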